3.2. Randomization

Randomization should only occur once subject eligibility is confirmed and will be conducted via an automated interactive response technology (IRT) to assign subjects to investigational product.

All treatment groups will be studied concurrently. A total of 1500 randomized subjects are planned for inclusion in the study: 750 subjects per group.

The following procedures will be performed prior to the injection:

- Assessment of inclusion and exclusion criteria
- Pregnancy test (performed locally, using central laboratory supplies) (women of childbearing potential only)
- Randomization
- Neurological examination (Protocol Appendix C)
- Vital signs: blood pressure and heart rate ([Section 3.8.3](#))
- 12-lead ECG
- Fasting lipid profile/biomarkers ([Section 3.9](#))
- Central clinical laboratory (full serum chemistry, hematology and coagulation) ([Section 3.8.8](#))
- Urinalysis (performed locally, using central laboratory supplies)
- Assessment of ADA ([Section 3.8.8.7](#))

The following procedures will be performed after the injection:

- Vital signs: blood pressure and heart rate (4 hours after injection) ([Section 3.8.3](#))
- Collection and storage of serum samples for possible future use to detect the formation of ADA (4 hours after injection)
- Concomitant medications
- AE/SAE reporting

Investigational product administration will occur at this visit for all subjects as per Protocol Section 5.1.1 and the Pharmacy Manual.

Subjects must be observed in the clinic for at least 4 hours after injection.

Should a subject develop signs or symptoms of anaphylaxis when investigational product is injected, the investigator will need to collect a blood sample for tryptase within 30 minutes of the onset of anaphylaxis (or as soon as logically possible).

If a local reaction around the injection site occurs that requires the patient be seen between visits or if a reaction is noticeable on a subsequent visit, photographs of the injection site should be obtained at first presentation and at each of the follow-up visits until the injection site reaction resolves, if possible. Photographs should be submitted to the study inbox of global safety office at The Medicines Company.

Detailed instructions for investigational product administration are found in the Pharmacy Manual.

3.3. Day 30 Visit

Subjects will return to the clinic for a follow-up visit 30 days following the first dose of investigational product. The following assessment will be completed during this visit:

- Assessment of ADA ([Section 3.8.8.7](#))
- Concomitant medications
- AE/SAE reporting

3.4. Additional Dosing Visits (Days 90, 270, and 450)

Subjects will return on Day 90 for a second investigational product injection. Subsequent investigational product injections will be administered on Day 270 and Day 450.

The following assessments will be completed during these visits prior to investigational product administration:

- Pregnancy test (performed locally, using central laboratory supplies, if applicable) (women of childbearing potential only)
- Vital signs: blood pressure and heart rate ([Section 3.8.3](#))
- Fasting lipid profile/biomarkers ([Section 3.9](#))
- Collection and storage of serum samples for possible future use to detect the formation of ADA ([Section 3.8.8.7](#))
- Central clinical laboratory (limited serum chemistry) ([Section 3.8.8](#))
- Concomitant medication
- AE/SAE reporting

Administration of the investigational product is identical to Day 1 and is per Section 5.1.1 of the protocol and the Pharmacy Manual.

Subjects must be observed in the clinic for at least 30 minutes after injection.

Should a subject develop signs or symptoms of anaphylaxis on days when investigational product is injected, the investigator will need to collect a blood sample for tryptase within 30 minutes of the onset of anaphylaxis (or as soon as logically possible).

3.5. Additional NON DOSING Clinic Visits (Days 150, 330, and 510)

Subjects will return to the clinic for dosing follow-up visits 60 days following each dose of investigational product. The following assessments will be completed during these visits:

3.5.1. Day 150

- Fasting lipid profile/biomarkers ([Section 3.9](#))
- Assessment of ADA ([Section 3.8.8.7](#))
- Central clinical laboratory (limited serum chemistry and hematology and coagulation) ([Section 3.8.8](#))

- Concomitant medications
- AE/SAE reporting

3.5.2. Day 330

- Fasting lipid profile/biomarkers ([Section 3.9](#))
- Assessment of ADA ([Section 3.8.8.7](#))
- Central clinical laboratory (limited serum chemistry) ([Section 3.8.8](#))
- Concomitant medications
- AE/SAE reporting

3.5.3. Day 510

- Pregnancy test (performed locally, using central laboratory supplies, if applicable) (women of childbearing potential only)
- Fasting lipid profile/biomarkers ([Section 3.9](#))
- Assessment of ADA ([Section 3.8.8.7](#))
- Central clinical laboratory (limited serum chemistry) ([Section 3.8.8](#))
- Concomitant medications
- AE/SAE reporting

3.6. End of Study (EOS) Visit (Day 540 – 90 days post last dose)

A subject's participation in the study is complete when the final visit, 90 days after the last dose of investigational product, has occurred. The following assessments will be completed during this visit:

- Pregnancy test (performed locally, using central laboratory supplies, if applicable) (women of childbearing potential only)
- Physical examination (including weight and waist circumference)
- Neurological examination (Protocol Appendix C)
- Vital signs: blood pressure and heart rate ([Section 3.8.3](#))
- 12-lead ECG
- Fasting lipid profile/biomarkers ([Section 3.9](#))
- Collection and storage of serum samples for possible future use to detect the formation of ADA ([Section 3.8.8.7](#))
- Central clinical laboratory (full serum chemistry, hematology and coagulation) ([Section 3.8.8](#))
- Urinalysis (performed locally, using central laboratory supplies)

- Concomitant medication
- AE/SAE reporting
- All ongoing SAEs have been followed to resolution

3.7. Interim Analysis

No interim analysis will be performed in this study.

3.7.1. Interim Safety Reviews

The IDMC will review safety data after the first 40 subjects receive the first SC injection of inclisiran or placebo and have completed one month follow-up. Thereafter the IDMC will review safety data every 3 months until the EOS unless requested otherwise by the IDMC. A recommendation may be taken to stop or amend the study at any of these reviews.

3.8. Assessment of Safety

3.8.1. Adverse Events

Subjects will be carefully monitored for AEs by the investigator during the designated study period (see [Section 4](#)).

3.8.2. Demographics and Medical History

Baseline demographic information will be collected during screening, and will include age, sex and race/ethnicity.

Relevant medical history includes all ongoing medical or surgical issues and any statin intolerance documentation. Remote medical and surgical history >5 years from the time of screening should only be included if considered relevant to the study.

3.8.3. Vital Signs

Vital signs include heart rate and blood pressure. When available, an automated blood pressure device is recommended for collection of blood pressure and the result recorded to the nearest mmHg. The subject should be sitting at rest for at least 5 minutes prior to these assessments. One assessment for each vital sign (heart rate and blood pressure) is required per applicable visit.

3.8.4. Physical Examination

The physical examination should include a focused examination, which may include general, respiratory, cardiovascular, abdominal, and extremities evaluations, and recording of weight, waist circumference, and height (baseline and EOS visit only). Significant changes from baseline will be collected as AE data.

3.8.5. Neurological Evaluation

A full neurological examination will be performed as per the Schedule of Assessment (Protocol Appendix C).

3.8.6. Electrocardiograms

Twelve lead ECGs will be collected at the time points in the Schedule of Assessments (Table 1) only, unless clinically indicated. Significant changes from baseline will be collected as AE data.

3.8.7. Cardiovascular Events

Information on CV events such as CV death, resuscitated cardiac arrest, non-fatal MI, and non-fatal stroke (ischemic and hemorrhagic) will be collected as AE data.

3.8.8. Clinical Laboratory Assessments

Specimens will be obtained at the time points in the Schedule of Assessments (Table 1).

Subjects will be in a fasted state for all clinical laboratory assessments. Screening laboratory tests will be performed by the Central Laboratory, with the exception of urinalysis and pregnancy test, which will be done in-house at the participating institution's laboratory using testing materials supplied by the Central Laboratory. Results from these screening tests related to eligibility must be available before the start of investigational product injection on Day 1 to confirm subjects meet eligibility criteria. Details regarding the processing, shipping, and analysis of samples will be provided in the Laboratory Manual. Note: Efficacy laboratory assessments (e.g., LDL-C and PCSK9) are described in Section 3.9.

3.8.8.1. Hematology

Blood draws for hematology will include:

- Hemoglobin, hematocrit, erythrocytes, reticulocytes, mean cell hemoglobin (MCH), mean corpuscular volume (MCV), mean corpuscular hemoglobin concentration (MCHC), platelet count, white blood cell count with differential.

3.8.8.2. Coagulation

Blood draws for coagulation will include:

- Prothrombin time (PT), international normalized ratio (INR), activated partial thromboplastin (aPTT).

3.8.8.3. Chemistry

Blood draws for chemistry will be performed per the Schedule of Assessments (Table 1).

Analysis will vary based on visit day as follows:

- **Full serum chemistry - Baseline (Day 1) and EOS (Day 540)**
Aspartate aminotransferase (AST), alanine aminotransferase (ALT), alkaline phosphatase (ALP), gamma glutamyl transferase (GGT), total bilirubin (TBIL), direct and indirect bilirubin, creatine phosphokinase (CPK), lactate, bicarbonate, uric acid, creatinine, blood urea nitrogen (BUN), estimated glomerular filtration rate (eGFR), sodium, potassium, calcium, inorganic phosphate, chloride, albumin, total protein, glucose (fasting), glycated hemoglobin A1C (HbA1c), and tryptase (as required).

- **Limited serum chemistry - Screening, Days 90, 150, 270, 330, 450 and 510**
ONLY: AST, ALT, ALP, GGT, TBIL, CPK, creatinine, eGFR, fasting glucose, HbA1c (not at Day 150, 330, and 510) and tryptase (as required).

3.8.8.4. Inflammatory markers (IL6, IFN- γ , and TNF- α , hsCRP)

The hsCRP is performed routinely for safety throughout the study and is part of the central laboratory draws.

Tryptase and other inflammatory markers such as interleukin 6 (IL6), interferon-gamma (IFN- γ) and tumor necrosis factor-alpha (TNF- α) may be performed from centrally stored sample aliquots at a later date, as required. Should a subject develop anaphylaxis on days when inclisiran is injected, the investigator will need to collect a blood sample for tryptase within 30 minutes of the onset of anaphylaxis (or as soon as logically possible).

3.8.8.5. Urinalysis

Urinalysis will be performed at the time points defined in the Schedule of Assessments (Table 1) and evaluated by dipstick analyses at the investigational site (a standardized dipstick test will be supplied by the Central Laboratory). Urinalysis will be performed from a sample of mid-stream urine. In case of abnormal results, microscopy and other assessments will be performed at the local laboratory and the abnormality recorded as an AE.

The following parameters will be assessed:

- Nitrite, protein, glucose, ketone, urobilinogen, bilirubin, red blood cells/erythrocytes, white blood cells/leukocytes, pH, urine sediment (microscopic examination will be only performed in the event of abnormalities).

3.8.8.6. Urine Pregnancy

Urine pregnancy testing will be performed locally at the visits specified in the Schedule of Assessments (Table 1), using the supplies provided by the Central Laboratory.

3.8.8.7. Anti-drug Antibodies

A serum sample for analysis of the induction of antibodies will be collected at the time points in the Schedule of Assessments (Table 1). Collection will be prior to and 4 hours after first investigational product administration (injection) and then as per the Schedule of Assessments. As presented in Section 3, serum samples for analysis are collected at every visit but assessment of ADA will only occur for samples collected at the following visits: Randomization (prior to injection), Day 30, Day 150, Day 330, and Day 510. Samples will be stored for assessment (if needed) for samples collected at the following visits: Randomization (after injection), Day 90, Day 270, Day 450, and the End of Study Visit.

3.8.9. Stored samples

The central laboratory will take aliquots of serum and plasma samples from the received routine blood sampling noted above and will store these as frozen samples to permit future analysis of the effect of inclisiran on the expression of these exploratory biomarkers. Analyses may include markers of CV risk (eg, hsCRP, IL6, P-selectin, Lp-PLA2, adiponectin). Biological samples for

biomarker research will be retained on behalf of the Sponsor for a maximum of 1 year following the last subject's last visit in the study. Details regarding the collection, processing, storage, and shipping will be in the Study Laboratory Manual.

3.9. Assessment of Efficacy

Subjects will be in a fasted state for all efficacy laboratory assessments of lipids/lipoproteins/biomarkers. Specimens will be obtained at the time points in the Schedule of Assessments (Table 1). Pharmacodynamic parameters to be assessed will include:

- Total cholesterol (TC), triglycerides, LDL-C, HDL-C, non-HDL-C, VLDL-C, Apo-A1, ApoB, lipoprotein (a) [Lp(a)], hsCRP, and PCSK9.

Directly measured (using ultracentrifugation) LDL-C will be done at baseline and at Day 510.

Calculated LDL-C will use the Friedewald calculation, as the Friedewald equation ($LDL-C = TC - HDL-C - TG/5$) is typically used in clinical practice.

Blood samples for determination of LDL-C concentrations will be collected at the time points in the Schedule of Assessments (Table 1). Details regarding the collection, processing, shipping, and storage of the samples will be provided in a Laboratory Manual.

Additional aliquots of plasma and serum will be collected at each time point and stored for additional analyses, including future analysis of biomarkers of CV risk. Plasma samples will be analyzed using a validated enzyme linked immunosorbent assay to determine PCSK9 protein concentration. Full details of the analytical methods used will be described in a separate bioanalytical report.

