The primary endpoints will use a reflexive LDL-C approach: either calculated LDL-C (based on the Friedewald formula) will be used, or if the calculated LDL-C is less than 40 mg/dL or triglycerides are greater than 400 mg/dL, or calculated LDL-C is missing, directly measured (using ultracentrifugation) LDL-C will be used if it is available.

Percentage change in LDL-C from baseline to Day 510

Missing values will be imputed for LDL-C after a reflexive approach using the multiple imputation (100 total imputed datasets) washout model specified in [Appendix 2](#). The percentage change in LDL-C at each visit will be calculated after the missing data imputation has been performed.

The primary analysis will be conducted on the ITT population and based on an ANCOVA model on the percentage change in LDL-C from baseline to Day 510 on each multiply imputed dataset (100 total). The model will include fixed effects of treatment group and current use of statins or other lipid-modifying therapies at baseline (yes or no) and baseline LDL-C as a covariate.

Treatment effects from these 100 ANCOVA analyses will then be combined using Rubin's Method via the SAS PROC MIANALYZE procedure. The difference in the least squares means

between treatment groups and corresponding two-sided 95% confidence interval will be provided for hypothesis testing.

See [Appendix 2](#) for more details on this analysis.

Time adjusted percentage change in LDL-C from baseline after Day 90 and up to Day 540.

A control-based pattern-mixture model (PMM), following the methods described in [Ratitch and O’Kelly \(2011\)](#), will be utilized to explore the possibility of data missing not at random (MNAR) for subjects who discontinued the study. For subjects who discontinued the study without any further follow-up data, their missing values after study discontinuation will be imputed under the assumption that their outcome would be similar to those in the placebo group with similar background characteristics. For subjects who did not discontinue the study, their intermittent missing values will be imputed based on the MAR assumption. Multiple imputations will be used to account for uncertainty in the imputation process and results from the imputed datasets will be combined using Rubin’s method [[Rubin, 1987](#)]. See [Appendix 3](#) for more details on this analysis.

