6.4.6.1.1. Sensitivity Analysis for Primary Efficacy Endpoints

In order to support the robustness of the conclusions drawn from the co-primary efficacy analyses, we will perform the following sensitivity analyses for the co-primary efficacy endpoints.

Percentage change in LDL-C from baseline to Day 510

- A control-based pattern-mixture model (PMM), using the same imputed datasets and MMRM model that was used for the second co-primary efficacy endpoint primary analysis will be used to compare treatments at Day 510. Multiple imputations will be used to account for uncertainty in the imputation process and results from the imputed datasets will be combined using Rubin’s method. (Refer to [Appendix 3](#) for details)
- A mixed model for repeated measurements (MMRM) analysis without multiple imputation, that assumes missing data are missing at random (MAR), will be performed. The model will include fixed effects for treatment, visit, baseline value, interaction

between treatment and visit, and current use of statins or other lipid-modifying therapies. The Restricted Maximum Likelihood (REML) estimation approach will be used with the covariance structure set as “Unstructured”. A linear contrast at Day 510 will be used to compare treatment groups. This will be the same model that is used as a sensitivity analysis for the second co-primary endpoint.

- The impact of country will be assessed by including country (possibly pooled into a region) and the treatment-by-country interaction fixed effects into the primary efficacy analysis ANCOVA (using multiple imputation washout model data).
- A tipping point analysis will be performed to search for the tipping point that reverses the study conclusion. In the tipping point analysis, we will independently vary the deltas in the treatment groups (inclisiran group progressively worse while the placebo group is not impacted and inclisiran group progressively worse while the placebo group progressively improves) until the hypothesis test on the co-primary efficacy endpoint becomes statistically insignificant. The MNAR(ADJUST) statement in SAS PROC MI will be used to adjust the delta of the imputed missing values analyzed using the ANCOVA model with washout model multiply imputed data.

Time adjusted percentage change in LDL-C from baseline after Day 90 and up to Day 540.

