APPENDIX 1. DETAILS OF MMRM USED FOR EFFICACY ANALYSES

A number of efficacy analyses will utilize a mixed-effects model for repeated measures (MMRM). This includes the co-primary efficacy endpoints (in the case of the first co-primary efficacy endpoint, it will be used as a sensitivity analysis), the key secondary efficacy endpoints, and other secondary efficacy endpoints.

The models will generally include fixed effects for treatment, visit, baseline value, interaction between treatment and visit, and current use of statins or other lipid-modifying therapies. The visits will include Days 90, 150, 270, 330, 450, and 510, with Day 510 as the primary time-point. Linear combinations of the estimated means will be created for the various hypothesis tests.

The Restricted Maximum Likelihood (REML) estimation approach will be used with the covariance structure set as “Unstructured.” The least squares means will be calculated for each treatment at each visit.

The analysis will be carried out using the SAS PROC MIXED procedure.

Sample SAS statements follow:

```
ods output LSmeans=estimates;
ods output Diffs=lsdiffs;
Proc Mixed Data=ldl_data;
  Class treatment visit_day subject_id statiny;
  Model percent_change = treatment|visit_day statiny
base_value/DDFM=KR;
repeated visit_day/type=UN subject=subject_id;
LSMeans treatment*visit_day/cl pdiff=control('0' '510');
run;
```

(where ('0' '510') is the value of the placebo ['0'] at day 510 ['510'] in interaction term treatment*visit_day)

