 2. The remaining missing values with a monotone missing data pattern will be imputed in this step. Control-based PMM imputation will be performed. With this imputation model, the missing efficacy measurements in the inclisiran group will not be constructed from the observed data in the inclisiran group but rather from the observed data in the placebo group. We will also use this model to impute missing efficacy measurements in the placebo group. The MNAR statement in SAS PROC MI will be used to impute missing values under the aforementioned assumptions. This will be performed for the 100 datasets. After this step, the 100 datasets will be fully imputed.
 3. A total of 100 fully imputed datasets will be created (M=100). Since multiple imputation is a stochastic method, slight differences in output can be expected for different initial states of the random number generator. The seed numbers will be identified in the SAS programs to allow for reproducibility.

4. After the missing data imputation is completed using the above steps, absolute change/percentage change values will be calculated in each of the imputed datasets at each visit.
5. These 100 datasets will be analyzed using the MMRM described in [Appendix 1](#) for the co-primary efficacy endpoints and key secondary efficacy endpoints.
6. Treatment effects (difference in LS means between treatments) from these 100 analyses will then be combined using Rubin's Method via SAS PROC MIANALYZE procedure for each endpoint.

APPENDIX 4. CRITERIA FOR POTENTIALLY CLINICALLY SIGNIFICANT AND CLINICALLY SIGNIFICANT ABNORMAL LABORATORY TESTS

Hemoglobin A1C criteria is explicitly stated in the table below.

All other criteria are met when both of the following occur:

- Post-baseline values meet the thresholds below
- Baseline values or any previous post-baseline values do not meet the thresholds below

Parameter	Unit	Lower Boundary	Upper Boundary
Hematology			
Hematocrit	%	$\leq 0.8 \times \text{LLN}$	N/A
Hemoglobin	g/dL	$\leq 10 \text{ g/dL}$	N/A
Platelet Count	$10^9/\text{L}$	$\leq 75^*$	$\geq 700^*$
White Blood Cell Count	$10^9/\text{L}$	≤ 2.8	≥ 16
Serum Chemistry			
Alanine Aminotransferase (ALT/SGPT)	U/L	N/A	$>1 \text{ and } \leq 3 \times \text{ULN}$
Alanine Aminotransferase (ALT/SGPT)	U/L	N/A	$>3 \text{ and } \leq 5 \times \text{ULN}^*$
Alanine Aminotransferase (ALT/SGPT)	U/L	N/A	$>5 \text{ and } \leq 10 \times \text{ULN}^*$

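### Does the reflexive LDL-C rule distort the time-adjusted co-primary endpoint, given that direct LDL-C is scheduled at only one of its averaged visits?

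*SAP*

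**What the plan says.** SAP Section 6.4.6.1 sets the measurement rule for both co-primary endpoints: "The primary endpoints will use a reflexive LDL-C approach". Calculated LDL-C is used by default. The direct result takes over "if the calculated LDL-C is less than 40 mg/dL or triglycerides are greater than 400 mg/dL", or when there is no calculated value; in those cases "directly measured (using ultracentrifugation) LDL-C will be used if it is available". The sentence stops there, with no clause for a trigger that fires when no direct value exists.

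SAP Section 3.9 gives the schedule for the direct assay: "Directly measured (using ultracentrifugation) LDL-C will be done at baseline and at Day 510".

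The first co-primary endpoint uses baseline and Day 510. The second averages the visits after Day 90 up to Day 540. In the Schedule of Assessments (SAP Table 1) the lipid draws in that span are Days 150, 270, 330, 450, 510 and 540. Appendix 1 gives a shorter list for the repeated-measures model: "The visits will include Days 90, 150, 270, 330, 450, and 510, with Day 510 as the primary time-point".

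Under the first co-primary endpoint, Section 6.4.6.1 adds "Missing values will be imputed for LDL-C after a reflexive approach". Section 6.4.6.1.1 opens with "we will perform the following sensitivity analyses for the co-primary efficacy endpoints" and then varies the imputation, the model, country, the averaging method and a tipping-point delta. It does not vary the LDL-C method.

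**The concern.** Two things look wrong.

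First, the time-adjusted endpoint mixes methods. Low values are replaced by direct ones at Day 510 but stay calculated at the other averaged visits. Low values will be almost entirely on inclisiran, so any difference between the methods would not cancel between arms.

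Second, the missing clause seems to leave room for a damaging interpretation. Imputation comes after the reflexive step. A programmer might therefore treat a calculated value below 40 mg/dL with no direct result as unusable and pass it to imputation. Appendix 3 would then fill the lowest inclisiran values from higher ones. A trailing gap at Day 540 could even be filled from the placebo model, since "The remaining missing values with a monotone missing data pattern will be imputed in this step". That would shrink a co-primary estimate by several points.

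**Working it through.** **1. Visit count.** Direct LDL-C is planned at one of six averaged visits (Day 510), or one of five on the Appendix 1 list, which omits Day 540. The premise is correct.

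**2. How the rule reads.** Four pieces of SAP text bear on a calculated value of, say, 35 mg/dL at Day 330 with no direct result.
- Section 6.4.6.1 makes the calculated value the default.
- It substitutes the direct value only where one is available, so without one the substitution does not occur.
- It lists a missing calculated value as a trigger separate from a low one, so a low value is not itself a missing value.
- Section 6.3.4.1 defines missing data as data not available from any scheduled or unscheduled visit. The 35 mg/dL result is available.

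Placing imputation after the reflexive step orders the operations; it deletes nothing. The value is kept.

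**3. How often it arises.** Entry is allowed from 70 mg/dL (Protocol Section 4.2), and the expected reduction is about 50 to 55% (Protocol Section 1.2.2.2). A subject falls below 40 mg/dL when baseline is below 40/(1 − 0.50) = 80, or 40/(1 − 0.55) = 88.9 mg/dL. Assumed inputs, not in the documents: mean baseline 104–121 mg/dL with none below 70, reduction 45–55% with SD 22 points, noise SD 5 mg/dL in the calculated value, the direct value taken as true. With no assay bias, 22–43% of inclisiran values and 0.5–0.8% of placebo values then fall below 40. It is common and one-sided.

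**4. Size of the method mix when low values are kept.** Planned mix against all-calculated:

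shift = between-arm mean of [(calculated − reflexive)/baseline] at Day 510, divided by 6 (or 5) visits.

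- No bias: 0.05–0.08 points. Only noise around the 40 mg/dL cut contributes.
- Calculated value reading 3–5 mg/dL low when true LDL-C is below 60: 0.2–0.6 points.

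Hand check at the high end: 43% × 5/104 = 2.07 points at Day 510, and 2.07/5 = 0.41 points averaged. The simulation goes somewhat higher because the bias pushes more values below 40.

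For the first co-primary endpoint, reflexive against direct at both visits gives 0.2–0.3 points less reduction with no bias, and 0.3–0.7 more with that bias.

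**5. Yardsticks.** Evaluable subjects: 1500 × 0.95 = 1425, about 712 per arm. The 95% half-width at one visit is 1.96 × 22 × √(2/712) = 2.29 points. For an average of six visits with within-subject correlation 0.6 it is 2.29 × √((1 + 5 × 0.6)/6) = 1.87. On the plan's own effect and SD, 30/(20 × √(2/712)) ≈ 28 standard errors, so neither test is at risk.

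**6. The reading that would hurt.** Suppose low values away from Day 510 were set to missing and imputed. With the step 3 inputs and within-subject correlation 0.5–0.7, the treatment difference shrinks by 3.8–10.8 points. A separate simulation (baseline means 99–128, SD 20, correlation 0.6) gives about 3–9 points for within-arm imputation alone. These figures are real, but they describe a step that step 2 shows the SAP does not call for.

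**The case for a change.** The best case for a change is that the retained value is inferred, not written. If a programmer inferred otherwise, the error would exceed the confidence half-width. One sentence would settle it at no cost, and would also cover triglycerides above 400 mg/dL, where the same clause is absent. It is true that the sentence is missing. But the default, the availability condition, the separate missing-value trigger and the missing-data definition all point the same way. Discarding an observed result would need an instruction, and there is none. Even the Day 540 fill from placebo sits badly with Appendix 3's opening, which reserves that assumption for subjects who left the study without further follow-up.

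A second objection concerns accuracy rather than wording: if calculated LDL-C reads low in this range, the visits without direct values overstate the reduction. Compared with direct replacement at every visit, assumed offsets of 2, 5 and 10 mg/dL below 40 give 0.3–0.8, 0.7–2.0 and 1.3–4.0 points on a difference of 45–55. The documents give no offset, so this cannot be narrowed. It is a limit of the assay schedule. Clearer wording would not alter it, and a calculated-only run would move further from the direct method. Section 3.9 plans direct values at baseline and Day 510, so the offset can be described from data already collected. ApoB, total cholesterol and non-HDL-C, none of which uses the Friedewald formula, are key secondary endpoints.

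Finally, the reflexive rule may imply triggered direct testing at other visits under the Laboratory Manual, which is not among the documents. That would only shrink the issue.

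**Conclusion.** The observations are accurate: one averaged visit with planned direct LDL-C, no explicit clause for a trigger without a direct result, and no method sensitivity analysis. They do not call for a change. Read as a whole, the SAP keeps the calculated value. The resulting mix moves the time-adjusted estimate by well under 1 point against all-calculated values: 0.05–0.08 with no bias, 0.2–0.6 with an assumed 3–5 mg/dL bias. Neither superiority test is affected. The 3.8–10.8 point loss belongs only to a reading that the text disfavours. The missing clause is a detail that analysts would fill sensibly, and extra runs by LDL-C method would be descriptive, changing no conclusion. All sizes rest on assumed baseline, variability and assay inputs. The reading of the rule does not.
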